### **1.6 Study Variables**

#### **A. Independent Variables, Interventions, or Predictor Variables**

Our IV of interest is treatment assignment; please see section 1.3 for a description of the study interventions.

#### **B. Dependent Variables or Outcome Measures**

Our DVs of interest are as follows: (1) pre-treatment to one-month follow-up change in (1a) motivation to quit (i.e., motivation), (1b) readiness to quit, and (1c) confidence in quitting; (2) setting a quit date (yes/no); (3) making a cessation attempt (yes/no); (4) days of self-reported abstinence, and (5) achieving initial CO verified abstinence (yes/no).

### **1.7 Drugs/Devices/Biologics**

- 1) *Nicotine replacement therapy.* Nicotine patch and nicotine lozenge are accepted, FDA approved treatments for nicotine dependence. Both are available over-the-counter (OTC) without a prescription. Study participants will be provided with information written at a 6th grade level describing the proper use of the nicotine patch and lozenge, including a description of common side effects. To minimize adverse events, we are excluding smokers with potential contraindications (see *Participants* section within *Methods* above).
  - a) *Storage and accountability.* We will store nicotine replacement therapy (NRT) in original packaging (box containing 2-week supply) in locked cabinets in a room with locked doors at [name] and at Institute for Health, Rutgers, The State University of New Jersey [name]. We will document temperature of the room weekly using a min/max thermometer.
    - a. *Transferring medication.* Research coordinators, [name] and [name], will arrange to transfer medication between research laboratory sites as needed. [name] and [name] will be the only people who transfer medication between sites, arranging with one another to pick up or drop off the medication.
  - b) *Inventory.* We will use an NRT inventory log to document the Lot # and Expiration date of each box of NRT.
  - c) *Dispensing NRT.* We will use an NRT dispensing log to document which boxes of NRT are provided to which subjects (listed by subject number only), by whom, and on what date. We will not collect unused portions of the NRT because it is not common practice to specify a time limit by which participants are required to use the NRT.
    - a. In the event NRT is stored at the Institute for Health, the research coordinators will arrange to pick up the medication or to drop off the medication at [name] for research subjects.

### **1.8 Primary Specimen Collection**

**A. N/A**

**B. N/A**

Protocol version: 03.15.2019

PI Name: [name].

Protocol Title: Addressing Tobacco Among  
Public Housing Residents

6

RESERVED FOR IRB STAMP  
DO NOT MODIFY THIS SPACE

RUTGERS | eIRB  
APPROVED

IRB ID: Pro20170000679

Approval Date: 3/25/2019

Expiration Date: 3/24/2020

C. N/A

D. N/A

E. N/A

### **1.9 Interviews, Focus Groups, or Surveys**

#### **A. Administration**

Following consent, study staff will first verify each participant's smoking status via expired breath carbon monoxide (CO > 5ppm). Participants will complete a questionnaire battery online via Qualtrics, using a laptop computer or tablet provided by study staff (see Table 1 below). If any participant indicates high levels of depression, we will provide phone numbers and a recommendation to contact Rutgers University Behavioral Health Care or the Rutgers RWJMS Department of Psychiatry outpatient practice.

**Timing and Frequency:** Following an initial phone screen, participants will be visited by study staff for an in-person session that will last approximately 60-90 minutes (including assessment and intervention). After randomization and Visit-1 study procedures are completed, they will be scheduled for a final follow-up visit to occur approximately one-month later.

**Location:** Study participation will take place at the Rutgers RWJMS Division of Addiction Psychiatry / Tobacco Research & Intervention lab, at the New Brunswick Housing Authority offices and / or housing units, or on the premises of the non-profit agency, Elijah's Promise, depending on study patient preference.

**Procedures for Audio Recording:** Participants will be asked permission to allow study staff to audio record their intervention as part of the research study, by signing the "Agreement to Audio Record" at the end of the consent form. Participants do not have to agree to be recorded in order to participate in the main part of the study. The recording(s) will be used for clinical supervision, to validate the integrity of the counseling intervention, and potentially to later examine the relationship between what is said during the sessions and various clinical outcomes. The recording(s) will include the participant ID number and date of the research appointment. Digital audio files will be stored on password protected computers and the files themselves will be password protected and encrypted using the Advanced Encryption Standard 256 method (AES-256). Files will be linked with each participant's ID number. Files will be destroyed 6 years after the protocol is closed.

#### **B. Study Instruments**

Below, please find details regarding questionnaire and interview administration.

#### **Measures List**

##### **Online Measures (Qualtrics)**

**1) Demographic Questionnaire:** To obtain basic social support information as well as descriptive information including age, race, ethnicity, marital and SES status. Additionally, we will ask the place where they are completing the survey.

**2) Fagerström Test for Cigarette Dependence (FTCD; Fagerström, 2012):** 6-item scale use to evaluate the quantity of cigarette consumption, the compulsion to use, and nicotine dependence. The measure

has both yes/no items (scored as 1 or 0) and multiple-choice items (scored from 0-3). These scores are then summed to give a total score from 1-10 where the higher the score the more intense subject's the nicotine dependence is.

3) **Smoking History Questionnaire** (SHQ; Bonn-Miller & Zvolensky, 2005): 30-item questionnaire used to assess participants smoking history and patterns of use. Items pertain to smoking rate, age of onset of smoking initiation, and years being a daily smoker.

4) **Distress Tolerance Scale** (DTS; Simons & Gaher, 2005): 15-item scale used to assess participants' perception of their ability to tolerate mental distress. Items (e.g. "I can't handle feeling distressed or upset") answered on 5-point Likert-type scales ranging from (1) strongly agree to (5) strongly disagree evaluate participants' ability to experience and endure negative emotional states and includes scales that assess appraisal, tolerance, absorption, and regulation. This scale contains good psychometric properties, including high internal consistency. Because six of these items are included in the DII, below, this measure will be comprised of nine items.

5) **Distress Intolerance Index** (DII; McHugh & Otto 2011): 10 items (e.g. *I can't bear disturbing feelings*) rated on a five point Likert-type scale (0 = very little to 5 = very much for question 1, 1 = strongly agree to 5 = strongly disagree for questions 2-7, and 1 = absent to 5 = very strong for questions 8-10) assess individual differences in perceived capacity to withstand and tolerate general somatic and psychological distress. One item is pulled from the Anxiety Sensitivity Index (ASI), six items from the DTS, eight items from the FDS The DII demonstrates strong internal consistency reliability and concurrent validity, and evidence for construct validity.

6) **Generalized Anxiety Disorder (GAD-7)**; Spitzer et al., 2006): 7-item index is a valid and efficient tool for screening for GAD and assessing its severity in clinical practice and research.

7) **Kessler Psychological Distress Scale (K6)**; Kessler et al., 2002): This 6-item measure is a validated and brief index that is used to screen for the presence of mood and anxiety disorders.

8) **Snaith-Hamilton Pleasure Scale (SHAPS)**; Snaith et al., 1995): 14-item measure used to assess the ability to experience pleasure from typically rewarding activities. Participants rate the degree to which they believe that they would experience pleasure from hypothetical situations using a 4-point Likert type scale ranging from 0 = definitely agree to 3 = definitely disagree. The SHAPS appears to demonstrate good construct validity through its significant association with a latent dimension of anhedonia and test-retest reliability.

9) **Change Questionnaire** (Miller & Johnson, 2008): Measures ratings of importance of quitting and confidence in quitting on a 10-point Likert-type scale from 0=Definitely Not to 10 = Definitely.

10) **McArthur Scale of Subjective Social Status** (Adler & Stewart, 2007): Self-report measure of an individual's sense of social status across different SES indicators. The scale is in a pictorial format, and presents the participant with a "social ladder" and asks them to place an "X" where they feel they fall. There are two separate social ladders that are presented to the participant. One is linked to traditional

SES factors, SES Ladder, while the other is linked to social standing within a community, Community Ladder.

11) **Readiness to Quit Ladder:** Single-item measure that includes ten response options that assess motivation to quit along a continuum. Options range from 10, "I have quit smoking and I will never smoke again", to 1, "I enjoy smoking and have decided not to quit smoking for my lifetime. I have no interest in quitting". As such, higher scores on this measure indicate higher readiness to quit.

12) **Stages of Change Algorithm** (Prochaska, Velicer, DiClemente, & Fava, 1988): This three item measure is used to assess readiness for change (i.e., smoking cessation) and will be used to categorize participants into precontemplation (i.e., not thinking about quitting), contemplation (yes, within next 6 mo.), and preparation (i.e., yes, within the next 30 days). This will then be used to inform therapist provided brief motivational interviewing.

13) **Financial Strain Scale** (Pearlin, Menaghan, Lieberman, & Jullan, 1981): This 9-item measure will be used to assess participants' perceptions of financial strain. Subjective indices of financial strain, rather than using education or income as the primary indicators of socioeconomic status have the advantage of assessing perceived burden and interference. On this measure eight items are rated on a 3-point scale (1=no difficulty to 3-very great difficulty; e.g., How difficult is it to afford a home suitable for (yourself/your family?). The final item asks participants to report how much money they have left over at the end of each month.

14) **Subjective Financial Situation Scale** (Williams et al., 2016): This single item measure asks participants to describe their subjective view of their overall personal financial situation.

15) **Attitudes Toward Nicotine Replacement Therapy scale:** This measure assesses previous offering of nicotine replacement therapy (NRT), perceived advantages to NRT use, perceived side effects, and if relevant, reasons for not using NRT.

16) **Quitting Preparation and Actions Questionnaire.** This measure is used at followup only and assesses actions consistent with preparing for or making an attempt to quit smoking.

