#### B. Hypotheses / Research Question(s)

Brief advice to quit (i.e., referral), brief motivational interviewing, and nicotine replacement therapy are recommended approaches to promote smoking cessation and reduce health disparities in low-income smokers (Fiore et al., 2008). However, as compared to referring participants to the NJ Quitline, we expect brief MI and provision of NRT to be superior in terms of: (1) Increasing motivation to quit; (2) increasing self-efficacy to quit; (3) setting a quit date; (4) making a cessation attempt; (5) and achieving initial abstinence.

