##### **Inclusion Criteria**

Participants must be between the age of 19 and 65, must self-report being a daily smoker and provide biochemical verification of smoking status (expired breath carbon monoxide reading >5), must be at socioeconomic disadvantage, defined as receiving services at a New Brunswick, NJ based social services agency (i.e., living in New Brunswick Housing Authority-run public housing units or requesting social services from the community social service agency, "Elijah's Promise"), and must be able to speak and read English.

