Outcome 4: Motivation and Self-efficacy for quitting smoking measured via Importance, Confidence, & Readiness Questionnaire" (rated on a 0 to 10 scale)

We will use separate Analysis of Covariance (ANCOVA) to examine differences in a) Self-reported Importance of quitting, b) Self-reported Confidence in one's ability to quit, and c) Self-reported Readiness to quit at the 1-month follow-up between participants randomized to the three intervention groups. Baseline ratings of motivation to quit will be included as a covariates.

Outcome 5: "Readiness to Quit Ladder" (with 10 non-numbered choices reflecting varying degrees of readiness

We will use Analysis of Covariance (ANCOVA) to examine differences in cigarettes smoked per day at the 1-month follow-up between participants randomized to the three intervention groups. Baseline score on the Readiness to Quit Ladder will be included as a covariate.

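### The Readiness to Quit Ladder awards its top score for having quit, so a quit-rate difference between arms can show up as a readiness difference, and the plan does not separate the two

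*Protocol*

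**What the plan says.** Protocol 1.9 B (Measures List, item 11) describes the Ladder as a "Single-item measure that includes ten response options that assess motivation to quit along a continuum". Scores run from 1 to 10, and "higher scores on this measure indicate higher readiness to quit". The option scored 10 is "I have quit smoking and I will never smoke again". The option scored 1 is a settled decision not to quit. The wording of the eight options between them is not given.

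Protocol 1.1 B lists "Increasing motivation to quit" as hypothesis 1 and initial abstinence as hypothesis 5. Protocol 1.6 B likewise keeps readiness (outcome 1b) apart from CO-verified abstinence (outcome 5). Under the inclusion criteria in 4.2 D, participants "must self-report being a daily smoker and provide biochemical verification of smoking status".

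The SAP makes the Ladder its Outcome 5, with choices "reflecting varying degrees of readiness", and names the baseline Ladder score as the covariate. The variable that its analysis sentence proposes to compare is cigarettes per day at one month. The SAP's other outcomes are a serious quit attempt, treatment contact, cigarettes per day, and 0-to-10 ratings of importance, confidence and readiness (Outcome 4). Abstinence is not among them. Neither document recodes, counts or separately reports people who have quit when they answer the Ladder.

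**The concern.** The top score reports a change in behaviour together with an intention, while the scale is described as measuring motivation. At baseline all participants should fall below that score. At one month anyone who has quit may move to it. The between-arm contrast on the Ladder then mixes two things: how ready the continuing smokers are, and how many people stopped smoking. Adjusting for the baseline score cannot undo this, because nobody has quit at baseline.

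What is at stake is interpretation. If NRT sampling helped people stop by easing withdrawal, the Ladder could rise in that arm and be reported as increased motivation. It would look like separate support for hypothesis 1 while partly repeating a smoking outcome. In the protocol that outcome is abstinence. In the SAP it is cigarettes per day (Outcome 3), where a quitter scores zero. Protocol 6.1 B says the pilot's data will be used to estimate effect sizes for a larger application, and the SAP reports *f*. A shift in means enters those estimates whether or not a test is significant.

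**Working it through.** The plan states no figure for the Ladder, so there is none to reproduce.

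**Inputs from the documents:** maximum score 10, awarded for having quit; all participants daily smokers at baseline; three arms with a target of 20 each (Protocol 1.5); ANCOVA with baseline Ladder as covariate (SAP Outcome 5, read as intended for the Ladder).

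**Assumed inputs:** quit rates, the mean *m* and SD of smokers' Ladder scores, the correlation with baseline, and that every quitter chooses 10.

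**Step 1: shift in the arm mean.** Let smokers average *m* in every arm, and let a fraction *q* of an arm quit and score 10. The arm mean is (1 − q)·m + 10·q = m + q·(10 − m). The difference between two arms is therefore

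(quit-rate difference) × (10 − m).

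| Assumed m | 10-point gap | 20-point gap |
|---|---|---|
| 5 | 0.10 × 5 = 0.5 | 0.20 × 5 = 1.0 |
| 6 | 0.10 × 4 = 0.4 | 0.20 × 4 = 0.8 |
| 7 | 0.10 × 3 = 0.3 | 0.20 × 3 = 0.6 |
| 8 | 0.10 × 2 = 0.2 | 0.20 × 2 = 0.4 |

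Strictly, *m* here is the score the additional quitters would have given had they kept smoking. If they come from the readier smokers, a lower row of the table applies and the shift is smaller.

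**Step 2: effect on the test.** Two simulations of the three-arm ANCOVA were run at the 5% level, with 4,000 trials per setting and smokers' readiness identical in all arms.

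- *20 per arm, SD 2, correlation 0.5, control quit rate 5%, both active arms equally higher.* With m = 6, rejection was 4.5% with no gap, 7.9% at +10 points and 20.9% at +20. Over m = 5 to 7 it was 7.9–8.5% at +10 and 17–22% at +20.
- *18 per arm, mean 6, SD 1.5, quit rates 5%, 15% and 25%.* The highest arm exceeded control by 0.81 points, and rejection was 17.8%.

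These are real differences in mean Ladder score. They mislead only if read as differences in motivation.

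**Step 3: effect of recoding.** If have-quit answers are set to the highest still-smoking option *c*, the shift becomes gap × (c − m), so a share (c − m)/(10 − m) remains. With m = 6 and c = 8 that is 2/4, or half: 0.20 × 2 = 0.4 points. The second simulation gave 0.41 points and 11.0% rejection. With c = 9 it would be 3/4. The true *c* cannot be read from the documents.

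**Step 4: continuing smokers only.** In the first simulation this brought the difference to about zero and rejection to 4.5–5.9%. That depends on quitting having been simulated as unrelated to readiness. In real data such an analysis conditions on a post-randomisation event and is no longer a randomised comparison.

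**The case against.** The strongest reply has four parts.

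- **Motivation already has its own measure.** SAP Outcome 4 is labelled motivation and self-efficacy and rates importance, confidence and readiness separately. Nothing says the Ladder is the test of hypothesis 1, and readiness in Protocol 1.6 B could equally be the Outcome 4 rating. This stands and lowers the stakes. It does not repair the Ladder, which Protocol 1.9 B still calls a motivation measure. The documents also do not say how a quitter should answer the Outcome 4 items.
- **The top option is more than behaviour.** It joins having quit to a resolve never to smoke again, so a recent quitter who is unsure need not choose it. This stands too, and it makes the Step 1 figures upper values for a given gap and *m*.
- **The gaps may be small.** The only effect sizes in the documents are *d* = .21 and .33 for MI on long-term cessation (Protocol 1.2). Using OR = exp(d·π/√3), these are odds ratios of about 1.46 and 1.82. With assumed control abstinence of 5–15% they imply gaps of roughly 2 to 9 points, or about 0.1 to 0.4 Ladder points at m = 6. No figure is given for NRT, so a larger gap cannot be excluded, but none is supported either.
- **It is a late outcome in a pilot.** Protocol 1.5 names quit attempts as the main outcome. This stands, and the point is an interpretive safeguard only.

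A reader might infer that the SAP counts abstinence twice, or that a Ladder difference would be spurious. The documents support neither. The SAP has no abstinence outcome, so its overlap is with cigarettes per day. A Ladder difference may reflect readiness, quitting or both.

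**Conclusion.** The point holds as a limit on interpretation. As planned, a quit-rate difference can appear as a Ladder difference, the baseline covariate cannot remove it, and nothing in either document lets a reader tell the two apart.

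The size is illustrative. With an assumed smokers' mean of 6 and all quitters scoring 10, it is about 0.4 points with 8% rejection for a 10-point gap, and about 0.8 points with 18% for a 20-point gap. Quit rates, Ladder mean and SD, and the middle options are all unknown. The mechanism is clear from the documents; its magnitude in this trial is not. It does not touch the main outcome, and it does not show the Ladder to be unusable. The Ladder should simply not stand alone as evidence that motivation rose.

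**What to change.** 1. Correct the SAP's Outcome 5 sentence first, so that it compares the one-month Ladder score. At present it names cigarettes per day, apparently carried over from Outcome 3, and the Ladder analysis is undefined until this is changed.
2. Report, by arm, how many participants choose any have-quit option.
3. Label the all-participant Ladder result a combined readiness-and-quitting score.
4. Add a supportive sensitivity analysis in all randomised participants with have-quit options recoded to the highest still-smoking option. Identify those options from the instrument itself, and state that recoding reduces the overlap without removing it.
5. Do not cite the Ladder alone as independent evidence for hypothesis 1. Rest that claim on the Outcome 4 ratings.

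The cost is a few sentences in the SAP and one extra model on data the trial already collects. The recoded score has a narrower range, so its effect estimates will tend to be smaller.

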### Pencil Paper Measures

1) **Initial screen:** This measure will allow us to determine if the participant is likely to meet inclusion criteria before we conduct a full baseline assessment.

2) **Timeline Followback** (Sobell & Sobell, 1992): method of assessing substance use requires participants to retrospectively estimate their daily substance and alcohol use. For the purposes of our study, we will be assessing past month alcohol, nicotine, marijuana, and other substance use.

3) **NRT Contraindication Checklist and Expired CO:** Participants will be screened for contraindications associated with NRT use, including: hypersensitivity to the active ingredient or any component of the NRT product, temporomandibular joint disease (should be excluded from using NRT gum), and active

gastric or duodenal ulcer (should be excluded from using NRT nasal spray) Any risks that may be associated with NRT are substantially outweighed by the dangers of continued smoking. Participants will provide expired breath carbon monoxide by blowing into the CO monitor to demonstrate smoker status (CO > 5ppm). CO levels will be documented on this form in parts per million (ppm).

4) **Adverse Events Questionnaires:** To be filled out by study staff during the follow-up visit with participants to assess AEs associated with quitting and use of NRT.

5) **Not Pregnant Form:** Using this form, women will state in writing that they are not pregnant or nursing, planning on becoming pregnant in the next two months, and that they are using effective birth control.

6) **Contact Form:** Participants will provide contact information to be used for scheduling appointments.

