**Visit 1:** Following the initial phone screen study staff will arrange to meet with eligible participants to administer additional measures as well as the brief intervention. In addition to verifying inclusion/exclusion criteria as well as smoking status, participants will be asked to complete a questionnaire battery online using a laptop provided by study staff, and a brief interview to further assess motivation and confidence to quit, substance use, physical health, and mental health status and history, as well as smoking cessation history.

**Study Interventions:** Next, we will use a block randomization procedure to allocate participants to one of three groups: A *single session motivational intervention (MI)*, which will include a 30-minute therapy session designed to enhance motivation to quit smoking, followed by a referral to the NJ State Quitline and local Tobacco Dependence Program; (2) An *NRT sample intervention*, which will include free two-week supplies of nicotine patches and nicotine lozenge with instructions for proper use and a referral to the NJ State Quitline and local Tobacco Dependence Program, or (3) An *assessment and referral only control*.

Block randomization is a procedure in which participants are randomly allocated to intervention groups within blocks such that an equal number are assigned to each intervention. We will use the Sealed Envelope Ltd. 2017 application to electronically develop a list of 60 allocation outcomes using a block randomization procedure with 3 intervention groups and block sizes of 3, 6, and 9. The study coordinator will use this list to inform study therapists of the intervention to which participants were assigned.

Upon completion of the intervention, participants will be scheduled for a one-month follow-up visit with a research assistant. Participants will be reminded of their appointment via text, phone, and email 48 and 24 hours prior.

**One-month Follow-up:** Participants will be asked to complete a brief online survey once again, and smoking status will be verified via self-report and carbon monoxide analysis of breath sample. Staff will also conduct brief interviews to assess main outcomes of interest.

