## **6.3 Data and Safety Monitoring**

### **A. Periodic Data Evaluation**

We conduct relevant interim data analyses at 1/3 (n=20), and 2/3 (n=40) of the way through data collection to examine differences between groups with respect to serious adverse events. If there is a significant difference in number of adverse events between groups, we will halt data collection and consult with the IRB.

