### **B. Type of Data Evaluated**

We will track reported adverse events using the Adverse Events Tracking log and categorize such events as mild, moderate and severe and take appropriate action accordingly, as determined by IRB guidelines for reporting. AEs and outcomes will be tracked using the Adverse Events Specifics log.

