### **C. Collection of Safety Information**

Participants will be queried regarding their experience of nicotine replacement at the follow-up session. Participants who report adverse events will be counseled on discontinuation.

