**G. Tests for Safety Data**

Analysis of variance will be conducted to determine if there are statistically significant differences between the three groups with regards to serious adverse events.

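### Serious adverse events are compared across three arms, but the events described as asked about are those of quitting and NRT, and no passage defines serious or maps a severity grade to it

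*Protocol*

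**What the plan says.** **What is compared.** Section 6.3 A of the protocol plans "interim data analyses at 1/3 (n=20), and 2/3 (n=40) of the way through data collection" to look at serious adverse events by group. Section 6.3 G plans an analysis of variance for "statistically significant differences between the three groups with regards to serious adverse events". Section 6.3 H says that such a difference would lead to a discussion with the IRB about suspending the research. The halting sentence in 6.3 A uses a different quantity: it turns on the count of adverse events, with no restriction to serious ones.

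**What is asked.** Two routes are described. The Adverse Events Questionnaires (section 1.9 B, Pencil Paper Measures) are "To be filled out by study staff during the follow-up visit with participants to assess AEs associated with quitting and use of NRT". Section 6.3 C adds: "Participants will be queried regarding their experience of nicotine replacement at the follow-up session".

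**Who receives NRT.** Under Study Interventions in section 1.3, only the NRT sample arm has an intervention "which will include free two-week supplies of nicotine patches and nicotine lozenge with instructions for proper use". The MI and referral arms receive none from the study.

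**How events are classified.** Section 6.3 B says that staff will "categorize such events as mild, moderate and severe and take appropriate action accordingly", as IRB reporting guidelines determine. It continues: "AEs and outcomes will be tracked using the Adverse Events Specifics log".

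The SAP contains no safety analysis.

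**The concern.** A between-arm comparison of harms needs the same ascertainment in every arm and a definition of the event being compared. The text supplies neither.

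First, both described routes ask about quitting or about NRT. People who were not given NRT have little to report to an NRT question, so the same symptom has a better chance of being prompted and recorded in the NRT arm. An admission in the MI or referral arm that has nothing to do with quitting or NRT is not something the described questions ask about.

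Second, mild, moderate and severe describe intensity. Seriousness is normally judged by outcome, such as hospital admission. A severe headache need not be serious, and an event of moderate intensity that leads to admission is. Without a stated link, whoever runs the comparison must improvise one.

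At stake is the only between-arm safety rule in the plan. The efficacy outcomes are not affected.

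**Working it through.** The plan states no adverse event rate, significance level, power or detectable difference for safety, so there is no figure to reproduce. The check is a side-by-side reading, followed by an illustration on assumed rates.

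**Reading**

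| Step | Protocol section | Events concerned |
|---|---|---|
| Elicitation form | 1.9 B | Events of quitting and of NRT use |
| Follow-up query | 6.3 C | Experience of NRT |
| Grading | 6.3 B | Mild, moderate, severe |
| Interim look | 6.3 A | Serious events |
| Halt, then consult IRB | 6.3 A | Number of events, not limited to serious |
| Test | 6.3 G | Serious events |
| Consult IRB on suspension | 6.3 H | Serious events |

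Two gaps follow. Nothing carries an event from the grading row to the serious-event rows. And 6.3 A and 6.3 H attach action to different sets of events, and different actions: a halt in one, a discussion about suspension in the other.

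**Illustration**

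- From the documents: 20 per arm, looks at n=20 and n=40, analysis of variance across three arms.
- Assumed: significance level 0.05; each participant scored 0/1 for any event; the same true event rate q in all arms; full capture in the NRT arm and a fraction c in the other two. The recorded rate is then q in the NRT arm and q × c elsewhere.
- Example: q = 0.40 and c = 0.50 gives 0.40 × 20 = 8 recorded in the NRT arm and 0.40 × 0.50 × 20 = 4 in each other arm at full size, with no true difference.

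Chance of a significant result (100,000 simulated trials per cell):

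| q and timing | c = 1 | c = 0.75 | c = 0.50 | c = 0.25 |
|---|---|---|---|---|
| 0.40, at either look up to n=40 | 9.1% | 12.4% | 25.5% | 53.7% |
| 0.40, one test at n=60 | 4.9% | 9.9% | 29.9% | 68.0% |
| 0.20, at either look up to n=40 | 8.0% | 8.4% | 12.6% | 24.1% |
| 0.05, at either look up to n=40 | 2.5% | 2.1% | 1.9% | 2.3% |
| 0.02, at either look up to n=40 | 0.4% | 0.3% | 0.2% | 0.2% |

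The c = 1 column is the baseline; for the looks up to n=40 it already includes the effect of testing twice. Only the excess over it comes from unequal capture: at q = 0.40 and c = 0.50, 25.5 − 9.1 = 16.4 percentage points by n=40.

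For rare serious events, the chance that none has occurred in any arm is (1 − q)^n. With q = 0.02 it is 0.98^20 = 67% at n=20 and 0.98^40 = 45% at n=40. With q = 0.05 it is 36% and 13%.

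So the consequence depends on which trigger in the protocol is meant. If all adverse events count, unequal capture can produce a false signal. If only serious events count, the test will seldom fire whatever the capture, and the weak points are the missing definition and the events not asked about.

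**The case against.** The strongest reply has four parts.

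- **Blinding.** Section 1.3 has the one-month contact made by an assistant blind to condition, so questions cannot readily be chosen by arm. The form also covers quitting, which can happen in any arm, and NRT is sold over the counter (section 1.7), so other arms may use it. This stands as a limit: capture is partly, not wholly, arm-dependent. It does not remove the point. An identical NRT question still yields less from people not given NRT, the answers may reveal the arm, and quitting is itself expected to differ by arm (section 1.1 B).
- **The logs.** A reader might infer that the logs have no place for seriousness. The documents do not support that. Neither log is reproduced, one is said to track outcomes, and IRB reporting guidelines are invoked. What can be said is that the logs are not described as holding a seriousness classification, and that no passage defines one.
- **Attribution.** A reader might infer that staff must decide cause before recording an event. No passage says so. Section 6.3 B tracks reported events without a causal filter, so an unrelated event volunteered by a participant could still be logged. The gap is in what is asked.
- **Size.** A reader might infer that questioning alone would create an excess of serious events in the NRT arm and stop the trial. The illustration does not show this: at serious-event rates of 2% to 5% the chance of a significant result by n=40 stays between 0.2% and 2.5% at every capture fraction tried.

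**Conclusion.** The point holds in a limited form. As described, ascertainment is at least partly arm-dependent, serious events unrelated to quitting or NRT are not asked about, serious is neither defined nor mapped from the severity grade, and section 6.3 A conflicts with 6.3 H on which events lead to action. These conclusions rest on the text alone.

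The size of any bias cannot be derived from the documents. The simulated figures rest on assumed event rates, capture fractions and a 0.05 level. They show only that unequal capture could matter for a count of all adverse events and would have little effect on a test of rare serious ones. This should be corrected, but it does not touch the efficacy analysis.

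**What to change.** In sections 1.9 B and 6.3 C, ask every participant in all three arms the same open question at follow-up, about any new or worsened health problem since Visit 1, before any NRT-specific item. In 6.3 B, record seriousness as an outcome-based yes/no field, separate from severity and from attribution. Report NRT-specific symptoms descriptively among NRT users.

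Sections 6.3 A, B, G and H must be reconciled by the authors on which events are compared and which lead to a halt or suspension. This review does not say which trigger is right.

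The cost is one question and one field at an existing visit, and a few more minor unrelated events recorded.

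That route may be closed: the SAP, dated September 2019, already reports five participants lost to follow-up, which suggests that follow-up is complete. If so, events never asked about cannot be recovered by adding a field. Classify the logged events for seriousness, state that elicitation was not uniform across arms, and present the between-arm adverse event comparison as descriptive only.
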